5.3 Concomitant Interventions

5.3.1 Allowed Interventions

N/A. Participation in this research study does not preclude use of any medications.

5.3.2 Required Interventions

N/A.

5.3.3 Prohibited Interventions

None

5.4 SBIRT-PM Fidelity Assessment

SBIRT-PM fidelity assessment will involve tracking the number of counseling sessions conducted per participant and the adherence and competence with which counselors conduct the sessions. All SBIRT-PM sessions will be recorded and counselors will maintain contact logs indicating all contact attempts made to participants, result of each contact, and duration of each counseling session.

Adherence and Competence: We will randomly select 220 audio recorded SBIRT-PM sessions from the total number of sessions occurring in the trial (maximum = 550 initial + 1650 follow-up sessions). Therefore, at a minimum we will have a 10% sample for validating that SBIRT-PM was delivered as intended. Specifically, the Independent Tape Rater Scale (ITRS) will be used to assess the degree to which SBIRT-PM sessions were delivered with fidelity to MI (i.e., with adherence and competence). The ITRS includes items that cover therapeutic strategies that are MI consistent (e.g. reflections) or inconsistent (e.g., unsolicited advice). For this trial, we added three general items that detail the extent to which strategies for pain and substance use occurred in the sessions. For each item, raters evaluate the counselors for adherence (i.e., the extent of intervention delivery) and competence (i.e., the skill/quality of intervention delivery) along 7-point Likert scales. We will: 1) calculate mean adherence and competence scores for the two factors (fundamental and advanced MI strategies) identified in prior psychometric analyses,^{96,100,101} and 2) determine if sessions achieve a criterion level for adequately performing MI, namely, at least half the MI consistent items rated average or above for both adherence and competence. In addition, we will evaluate the degree to which clinicians addressed pain and substance use during the session, based on our general items. We have documented experience training ITRS raters to perform reliable MI session process ratings in multi-site trials.¹⁰²⁻¹⁰⁶

For the data analyses, adherence to SBIRT-PM counseling will be dichotomized (“Having received counseling” Yes/No). This approach is being taken because SBIRT-PM’s duration and intensity is not hypothesized to relate to outcome; a Veteran might, in a single session, take steps to engage in non-pharmacological pain treatment that require minimal follow-up. Conversely, a Veteran with more follow-up sessions might have more because the Veteran is more ambivalent about non-pharmacological pain treatments and is receiving more counseling because of more need for it. After the completion of the intent-to-treat analyses, the adherence indicator will be added to examine it as a potential mediator of response in the primary outcome analyses.

6. STUDY PROCEDURES

6.1 Schedule of Evaluations

RCT Assessments

Assessment Name/Domain	Data Source	Baseline	12-wk	36-wk
Socio-demographic Characteristics	Self-Report	x		
Psychiatric and Substance Use Diagnoses	VA EHR -structured data (e.g. clinic codes)	x		
Characteristics of Musculoskeletal Disorders	VA EHR, Service-connection exam	x		
Distance to nearest VA Facility	VA EHR		x	
Brief Pain Inventory	Self-report	x	x	x
Numeric Rating Scale	Self-report	x	x	x
Opioid Medications Dispensed in Morphine Equivalent Daily Dose	VA EHR	x	x	x
Non-opioid Medications Dispensed	VA EHR	x	x	x
Non-pharmacological Pain Management Service Use—VA services	VA EHR -structured data (e.g. clinic codes)	x	x	x
Non-pharmacological Pain Management Service Use---VA and non-VA services	VA EHR with Natural Language Processing	x	x	x
Self-reported VA and non-VA service use	Self-report	x	x	x
ASSIST	Self-report	x	x	x
Prescription Opioid Misuse	Self-report	x	x	x
Nail clippings for drug/etoh use metabolites	Biological	x	x	x
Substance Use Treatment Service Utilization – VA services	VA EHR -workload data and clinic codes	x	x	x
Self-reported VA and non-VA substance use service use	Self-report	x	x	x
PHQ-9 (depression)	Self-report	x	x	x
EQ-5D -5L	Self-report	x	x	x
PEG	Self-report	x	x	x
Motivation for engaging in pain treatment	Self-report	x	x	x

High Impact Pain Questions	Self-report	x		
Audit-C	Self-report	x		
COVID-19 questionnaire	Self-report	x	x	x

UG3 Preparation Assessments and End-of-Study Assessments

Measures Described Earlier in UG3 Stage of RCT preparation	Data Source	UG3 preparation phase	End of Study
Qualitative Interviews of Stakeholders	Self-report	x	x
Post-intervention Interview of SBIRT-PM-treated Veterans	Self-report	x	
Relational Coordination Survey of Key Stakeholders	Self-report	x	x
Treatment Fidelity Measure: Independent Tape Rater Scale	audio recorded SBIRT-PM session ratings		x

6.2 Description of Evaluations

6.2.1 Screening Evaluation

A waiver of HIPAA authorization and waiver of informed consent have been obtained to access lists of Veterans applying for Compensation and Pension benefits for back/neck/knee/shoulder conditions at 8 study sites. Identified individuals who are post 9-11 status will be mailed a letter explaining the study. Individuals will be eligible for enrollment for up to 6 weeks after the letter was mailed. The SBIRT-PM intervention acts by engaging Veterans in pain treatment, and Veterans who have not engaged in three or more non-pharmacological pain treatment modalities (one of the inclusion criterion) still are at the stage of care that they could benefit from the proposed counseling.

Four days after the mailing, research assistants will follow-up the recruitment letters with a telephone call to fully screen Veterans for inclusion in the study using the participant screening form. Screening forms will be saved in the research study folder on the VA secure network. The screening evaluation after the letters are mailed consist of a few questions about pain treatments received, pain severity, and availability of a phone.

Individuals who meet all inclusion/exclusion criteria and are interested in participating in the study will be consented over the phone.

Consenting Procedure

A waiver of HIPAA authorization and a Waiver of Documentation of Informed Consent have been obtained to consent participants into the study. Research Assistants will consent eligible individuals into the research study by telephone call. Research Assistants will audio record the informed consent process for individual to enroll him/her into the study. Audio files of the informed consent process will be saved in the research study folder on the VA secure network.

6.2.2 Enrollment, Baseline, and/or Randomization

Enrollment

The enrollment date is that day the individual has met all the screening criteria and has agreed to participate in the study by completing audio-recorded informed consent.

Baseline Assessments

Measures to Characterize the Sample.

- Socio-demographic Characteristics. A research assistant will collect self-reported socio-demographics (age, sex, race, ethnicity, marital status, education, employment status, legal status, and military history) from Veterans during baseline assessment.
- Medical Diagnoses. We will extract medical diagnoses from electronic health records and the VA Corporate Data Warehouse. We will identify psychiatric (e.g., depression, anxiety, Traumatic Brain Injuries,^{107,108} and PTSD^{109,110}) and substance use disorders in the EHR and VA Corporate Data Warehouse by their ICD-9 and 10 codes. We decided against more direct measures of psychiatric conditions (e.g. the PTSD Checklist) to minimize participant burden and reactivity. To increase the sensitivity of our detection of psychiatric conditions, we will extract the service-connection claims data from the Veterans Benefits Management System for study participants at the end of their study participation. New recipients of service-connection receive it for an average of 5.25 distinct claims,⁴⁰ and many Veterans file both MSD and claims for mental conditions at the same time. This will identify Veterans with psychiatric disorders who were diagnosed during their service-connection examinations but do not have a diagnosis in VA treatment records because they were not treated for their mental health condition.
- Characteristics of Musculoskeletal Disorders. We will determine the diagnostic group of MSD assigned to participants in the EHR by using ICD-9 or 10 codes. Major groups are back pain, neck pain, and osteoarthritis. Other categories will be combined as suggested by their frequency and co-occurrence with other MSD. These include non-traumatic joint disorders, osteoporosis, sprain and strain, traumatic joint disorder, spinal cord injury, fibromyalgia, rheumatoid arthritis, temporal mandibular disorder, lupus, gout, and MSD multimorbidity (more than one MSD diagnosed). The broad MSD groups will be considered as potential moderators of treatment effect in the analyses. In addition, compensation examiners complete a detailed, structured form, the Disability Benefits Questionnaire (DBQ), for each Veteran they evaluate. From these forms, we will extract structured notations of the examination findings. Finally, we will obtain the final percentage service-connection awarded from the Veterans Benefits Administration System (VBMS) after the determination, and delineate service-connected conditions.

Pain Measures:

- Brief Pain Inventory (BPI). The Brief Pain Inventory¹¹¹ (BPI) is a validated instrument to assess chronic non-cancer pain that yields two subscales. One measures pain severity (4 items on a 0-10 scale) and the other assesses pain interference with life activities (7 items on a 0-10 scale), both using a 24-hour recall period. BPI pain

severity will serve as our primary pain outcome for the trial; pain interference will serve as a secondary outcome. The BPI is a reliable measure and responsive to change.¹¹² The BPI is endorsed by the Initiative on Methods, Measurement, and Pain Assessment in Clinical Trials (IMMPACT) group¹¹³ as a preferred measure of pain-related functioning. IMMPACT recommendations have specified score changes that would represent a minimally clinically important difference (i.e., 30% reduction in pain severity and 1-point reduction in pain interference), which will be used in our cost analyses.¹¹⁴

- Numeric Rating Scale (NRS). The NRS¹¹⁵ is an 11-point (0 = no pain, to 10 = worst pain imaginable) scale for current pain. It is the only pain measure collected at point-of-care for every Veteran as part of the vital signs assessment in Primary Care and entered into the EHR. The NRS has several shortcomings: a) Veterans may seek services when their pain levels are high, thereby masking longitudinal improvements in pain intensity; b) point-of-care contacts vary substantially among Veterans in Primary Care, rendering systematic analysis of changes in pain symptoms difficult to ascertain in a clinical trial; and c) point-of-care NRS significantly underestimates pain intensity compared to same-day paper-and-pencil NRS assessments.¹¹⁶ Balancing the ubiquitous use of NRS with its limitations, we will examine EHR-abstracted NRS ratings for participants as a secondary outcome.
- PEG¹¹⁷. The PEG is a 3-item scale assessing pain intensity (P), interference with enjoyment of life (E), and interference with general activity (G) during the past week. It has good reliability, constructive validity, and sensitivity to change and has been required by the NIH-DoD-VA Pain Management Collaboratory Coordinating Center as a common measure across funded protocols.
- High Impact Pain Questions. Three questions to determine the long-term impact of pain are being asked: “In the past 3 months, how often did you have pain?”; “Over the past 3 months, how often did pain limit your life or work activities”; “Are you not working or unable to work due to pain or a pain condition? Answer choices consist of “never”, “some days”, “most days” or “every day” for the first two questions and yes/no for the third question.

Pain Treatment Services Received:

- Opioid Medications Dispensed. We will extract dispensed opioid medications and dosages from the patient’s electronic medical record and convert them to morphine equivalent daily dose using the procedures from a published algorithm¹¹⁸ as adopted and operationalized by the PMC3 Phenotypes and Outcomes workgroup. Medications will be classified as opioids used to pain as follows:
 - (1) All non-IV fills of:
 - a) Codeine
 - b) Fentanyl
 - c) Hydrocodone
 - d) Hydromorphone
 - e) Morphine
 - f) Oxycodone
 - g) Oxymorphone
 - h) Tramadol

- (2) All non-IV, pill/tablet pills of:
 - a) Methadone
- (3) All transdermal or buccal fills of
 - a) Buprenorphine

MEDD is calculated by assuming prescriptions were taken as directed. Total morphine equivalents are calculated by multiplying the quantity of each prescription by the strength of the prescription (milligram of opioid per unit dispensed). Standard conversion factors on the CDC website will be used to estimate the number of milligrams of morphine equivalents dispensed. Average daily morphine equivalent dose will be calculated by dividing total milligrams of morphine equivalents by days supplied. For prescriptions that span a particular month, only dates during that month will be included.

The PMC3 Collaboratory recommends the following be collected, and we will collect and analyze them per their recommendations:

- a. Number of opioids supplied
- b. Days supplied
- c. a/b x conversion factor = milligrams morphine equivalent daily dose (MEDD)
- d. Mg MEDD at enrollment
- e. Mg MEDD monthly during enrollment and at study completion.
- Non-opioid Medications Dispensed. We will extract dispensed non-opioid pain-related medications from the medical record. These medications will include topical analgesics, non-steroidal anti-inflammatory drugs, anticonvulsants, and antidepressants (specifically, selective serotonin and norepinephrine reuptake inhibitors and tricyclic antidepressants). The presence or absence of medications in each class will be the dependent measure.
- Non-pharmacological Pain Management Service Utilization-VA Records. [name] and the PRIME Center have an algorithm for identifying visits from the EHR involving non-pharmacological management using workload information entered at clinic visits (e.g. diagnosis treated, procedure performed) and the type of clinic providing the treatment.
- Natural Language Processing-identified Non-Pharmacological Pain Management Service Utilization-VA and non-VA service use. This identifies dates at which the Veteran has reported “current use” of specific pain management modalities.
- Self-Reported Use of Pain Treatment Services. The PMC3’s phenotype and outcomes workgroup developed the “Use of nonpharmacological and self-care approaches” questionnaire to collect information about patients’ use of 13 different pain treatments, including Acupuncture, Rehabilitation Therapies, Manipulation, Massage, Yoga, Tai Chi/Qigong, Exercise, Biofeedback, Hypnosis/Hypnotherapy, Guided Imagery, Meditation, Psychotherapy/Counseling. In addition to asking about whether each treatment category was used, the instrument also includes questions about the most important reason for use, whether the treatment was received from a practitioner, the type of setting of use, how the service was paid for, how often it was used, and how effective it was in relieving pain. The instrument was modified for this study to collect information over the past 3 months (instead of past year), and to include several additional categories: Reiki, Pain School, Pain Clinic, primary care services, emergency/urgent care services, opiate and non-opiate medications.

Substance Use Measures:

- ASSIST. Substance use will be measured over the last 3 months using Version 3.1 of the Alcohol, Smoking and Substance Involvement Screening Test (ASSIST). After a screening question focusing on substances ever used, the ASSIST consists of seven questions about use of and consequences of use of each of ten classes of substances over the preceding three months (including nicotine). Scores are generated for each substance that are mapped to a three-point ordinal scale of severity.¹¹⁹ As outlined in the World Health Organization's Manual describing the use of the ASSIST to guide treatment recommendations, the ASSIST ratings are scaled to represent no need for treatment, need for a brief intervention, and need for an intensive intervention. An advantage of the ASSIST is that these categories represent what clinicians consider a clinically important difference, in that they guide treatment recommendations. The items in the ASSIST have been shown to have good to excellent reliability for the substances assayed. The reliability of the individual ASSIST items,¹²⁰ and the ASSIST's concurrent validity compared to other more detailed assessments of substance use severity¹²¹ have justified its adoption by the World Health Organization.¹²² We will obtain additional specifiers for substances requiring further characterization: a specifier about use of vaping for tobacco products, a specification as to whether the Veteran is using legal or prescribed cannabis and specification about use of prescribed amphetamine.
- Prescription Opioid Misuse. Two questions,¹²³ adapted from the CIDI¹²⁴ for use in a NIDA Clinical Trials Network study,¹²⁵ will be used to describe misuse of prescribed opioid medications: *“How often have you taken your pain medications in larger amounts than prescribed or for a longer period than prescribed?”* and *“How often have you used your pain medicines to get high, to relax, or to make you feel more alert?”* The questions are asked about the preceding 4 weeks, with follow-up questions to clarify that the question refers to opioids only.
- Nail Collection and Measurement. Nail clippings will be assayed for metabolites of alcohol (ethyl glucuronide i.e. ETG), cannabinoids (carboxy-THC, native-THC), opioids (6-MAM, codeine, hydrocodone, hydromorphone, morphine, oxymorphone, oxycodone), Amphetamines (amphetamine, MDA, MDEA, MDMA, methamphetamine), Cocaine (benzoylecggonine, cocaethylene, cocaine, norcocaine) and Phencyclidine (PCP). The tests are highly specific. Samples are analyzed using an immunoassay technique (ELISA) and non-negative specimens are subjected to a gold standard confirmation technique (GCMS or other method, depending on drug class). Nail, like hair, traps biomarkers in keratin but has higher concentrations of neutral and acidic biomarkers because it has thicker keratin. In a study of hair and nails collected from the same people, the rate of Carboxy-THC (an acidic biomarker for cannabis) positives for cannabinoid at the SAMHSA-recommended cutoff was 46.7% for hair and 53.3% for fingernails and mean concentrations of the metabolite were five-fold higher in nails than in hair.¹²⁶ In a study in the journal *Addiction* of 606 college students,¹²⁷ nail ETG at the 8 pg/mg threshold proposed for this study detected high-risk drinking with a sensitivity of 1.0 and a specificity of .63. Receiver operating characteristic curves were significantly higher for ETG concentration in fingernails than in hair for detecting risky drinking.

The biomarkers are incorporated throughout the nail plate from base to tip, by deposition of biomarkers from the capillary rich nail bed, thus allowing measurement by any nail clipping of sufficient weight. Biomarkers are thought to reflect 3-6 months of substance use history in fingernails, and toenails, which grow more slowly, reflect up to 9 months. The detection window (3-6 months) is close to the timeframe of the ASSIST (90 days), making cross-validation by the two measures reasonable.

Approximately 100 mg of nail is required for analysis, which can be obtained from 2mm (a quarter's width) of nail from each of ten digits. Samples will be mailed from home and thus un-observed, and participants will be provided with kits for the nail clipping, and a financial incentive of \$30 for providing each of the samples. We will also suggest Veterans set reminders to allow for growth before clippings are needed.

To reduce the risk that Veterans pass off someone else's fingernails as their own, they will be asked if the nails are theirs, and paid regardless of whether they are. Specimen substitution when there are contingencies for positive urines occurs, but there is no incentive for such false reporting when payment is provided regardless of the sample results. The samples will be mailed in coded envelopes addressed to our group, further reducing the likelihood of submitting someone else's fingernails.

- Samples will be processed at the United States Drug Testing Laboratories (Illinois). After processing, samples will be destroyed following a standard storage period. Sample analysis uses fully validated methods that have been inspected and approved by the College of American Pathologists Forensic Drug Testing Program and the New York State Department of Health. Substance Use Treatment Service Utilization-VA Records. Visits from the EHR involving substance use treatment will be identified conservatively, using an algorithm involving workload information entered at clinic visits (e.g. diagnosis treated, procedure performed) and the type of clinic providing the treatment. The measure does not capture much substance abuse counseling in primary care settings, and in conjunction with other mental health treatment (i.e., PTSD treatment). For this reason, self-reported substance use service utilization will be collected (see below).
- Self-Reported Use of Substance Use Treatment Services: Using the same format as the pain treatment service use questions described above, we will inquire about *whether* each of a number of classes of treatments was received in the preceding 12 weeks (substance use counseling, day program, residential, ER/hospital, self-help, counseling at a medical visit, counseling at a visit for a psychiatric condition, opioid substitution, smoking cessation counseling, nicotine replacement therapy prescribed).
- Alcohol Use Disorders Identification Test (AUDIT-C)¹²⁸. This is an alcohol screen used to identify patients who are hazardous drinkers or have active alcohol use disorders (including alcohol abuse or dependence). It consists of three questions: "how often did you have a drink containing alcohol in the past year?", "how many drinks did you have on a typical day when you were drinking in the past year", and "how often did you have six or more drinks on one occasion in the past year". It is scored on a scale of 0 (no use) through 12. In men, a score of 4 or more is considered positive and in women, a score of 3 or more is considered positive.

Other Measures:

- Patient Health Questionnaire (PHQ-9). The PHQ-9 is a well validated screening measure for depression¹²⁹ and will be used to identify probable depression as a covariate in analyses. It will also identify suicidal ideation, which if severe, will trigger the need for further assessment (detailed in Human Subjects).
- EQ-5D-5L. The EQ-5D-5L is a standardized measure of health status designed to provide a single index value of health for clinical and economic appraisals. It consists of five questions in the domains of mobility, self-care, usual activities, pain/discomfort, and anxiety/depression. ¹³⁰
- Motivation for engaging in pain treatment^{131,132}. Motivation for Change Scale to include 3 items (analogue scale coded from 1 to 100) tapping patient likelihood to engage in pain services, recognition of pain treatments as important, and pain treatment motivation.
- COVID-19 questionnaire. These questions will assess participant infection status, adherence to COVID-19 safety regulations, and the effect that COVID-19 regulations have had on Veterans' social determinants of health, access to pain treatment, and access to substance use treatment.

Qualitative Measures Collected in UG3 Phase and then again at the end of the UH3 Phase:

- Relational Coordination Survey. This survey, will be administered post-trial to "hub" SBIRT-PM clinicians and "spoke" clinical and administrative staff in Compensation and Pension and Primary Care to examine how pain care was coordinated to meet the treatment needs of compensation-seeking Veterans. It includes seven dimensions: frequency of communication, timeliness of communication, accuracy of communication, problem-solving, shared goals, shared knowledge, mutual respect). Respondents indicate the frequency in which each dimension exists in their setting on a 5-point scale. The mean of the individual scores serves as the overall RC score for each dimension within each spoke site.
- Post-Trial Semi-Structured Qualitative Interview. At the end of the trial, we will conduct in-depth interviews with "hub" SBIRT clinicians and "spoke" clinical and administrative staff in Compensation and Pension and Primary Care to assess the organization and coordination of pain management services, given their experiences with SBIRT-PM implementation.

Randomization

The urn randomization covariates are: site (8 sites of VISN1), sex (M/F), race (White, Black, Other), ethnicity (Hispanic/Non-Hispanic), and self-reported illicit drug use (Yes/No). Following enrollment and Baseline assessments, the Project Director will enter covariates into urn randomization program to determine intervention condition assignment. Randomization will occur within two weeks of the enrollment date.

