[name] (Research Coordinator), Central Western Mass VA, [name], [contact] [name], Email: [contact]

[name] (Research Coordinator), White River Junction VA, [name], [contact], Email: [contact]

[name] (Research Coordinator), White River Junction VA, [name], [contact], Email: [contact]

[name] (Biostatistician), [name], Department of Psychiatry, Yale School of Medicine. [contact], Email: [contact]

[name] (Collaborator), Palo Alto Veterans Institute for Research, [name], [contact], Email: [contact]

[name] (software developer), Washington DC VA Medical Center, [name], [contact], Email: [contact]

PARTICIPATING STUDY SITES

Hub

- Connecticut VA

Spoke

- Bedford VA
- Boston VA
- Central Western Massachusetts VA
- Maine VA
- Manchester VA
- Providence VA
- White River Junction VA

Other Sites Involved in Data Analysis

- Washington DC VA

PRÉCIS

Study Title

Engaging Veterans Seeking Service-Connection Payments in Pain Treatment

Objectives

Determine the effectiveness and cost-effectiveness of Screening, Brief Intervention and Referral to Treatment for Pain Management (SBIRT-PM) compared to Usual Care (UC) in reducing pain and risky substance use.

Design and Outcomes

In a pragmatic two-arm, parallel groups 36-week multi-site randomized controlled single blind trial, we will randomize 1100 Veterans applying for compensation related to musculoskeletal disorders to either SBIRT-PM or Usual Care (UC) across eight VA medical centers in New England.

Outcome assessment by phone will occur at 12- and 36-week follow-ups and will be corroborated with other sources of information --- the electronic health record and toxicology testing of nail clippings.

Primary outcomes will be change in pain severity as measured by the Brief Pain Inventory (BPI) and change in substances categorized as requiring intervention measured by the ASSIST. Secondary outcomes will include non-pharmacological pain management service utilization, NRS pain severity, pain interference with life activities as measured by the BPI, overall pain (PEG), overall health (EQ-5D-5L), use severity for individual substances generated by the ASSIST, and toxicology results for individual substances. The trial will include cost-effectiveness and budget impact analyses.

Interventions and Duration

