Screening, Brief Intervention and Referral to Treatment for Pain Management (SBIRT-PM) aims to engage Veterans applying for compensation with pain conditions in multi-modal non-pharmacological pain care and to motivate those who misuse substances to change this problematic behavior. SBIRT-PM will be delivered centrally by telephone throughout the New England VA Healthcare System's (VISN1) eight medical centers. It involves an initial one-hour session followed by up to three 20-minute calls in a 12-week period and an additional call in the 12-32 week period to support Veterans engagement in non-pharmacological pain care.

Usual care (UC): A Veteran who completes a compensation examination ordinarily has no further treatment, referral or debriefing as part of the Compensation examination

Sample Size and Population

The study sample consists of 1100 randomized post-911 era Veterans applying for MSD related compensation. Participants will be randomized using a computerized urn randomization program within each site to increase the likelihood of balanced allocation of participants to the two interventions on

sex, race, ethnicity and self-reported illicit drug use within 90 days.

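### The secondary NRS outcome is taken from clinic records, where treatment can affect who is rated and when, although the schedule lists a self-report NRS at the fixed assessments

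*Combined protocol and SAP*

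**What the plan says.** The combined protocol and SAP describes the NRS in four places that do not agree.

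- **Précis, Design and Outcomes:** "Secondary outcomes will include non-pharmacological pain management service utilization, NRS pain severity" and other measures. No data source is given.
- **Section 6.1, schedule:** the row reads "Numeric Rating Scale Self-report x x x", that is, self-report at baseline, week 12 and week 36. Rows drawn from records carry a VA EHR label; this one does not.
- **Section 6.2.2, Pain Measures:** the NRS is described as the rating taken "as part of the vital signs assessment in Primary Care and entered into the EHR", and the record-based rating is named as the secondary outcome: "we will examine EHR-abstracted NRS ratings for participants as a secondary outcome". The same bullet concedes that "Veterans may seek services when their pain levels are high, thereby masking longitudinal improvements in pain intensity" and that "point-of-care contacts vary substantially among Veterans in Primary Care". It also says that point-of-care ratings run lower than same-day paper ratings.
- **Sections 3 and 9.5.2:** the lists of secondary outcomes do not include the NRS.

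Section 9.6 gives no rule for which clinic ratings count, in what window, how several ratings are combined, or what happens to a Veteran without a visit. Under Sources of data, it says that missing medical-record data for Veterans who do not use VA will touch both arms and is not expected to differ between them. It plans a sensitivity analysis restricted to Veterans with records.

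**The concern.** A record-based NRS is observed only if the Veteran comes in. Coming in happens after randomization, and the intervention is meant to influence contact with care. The Précis says that SBIRT-PM "aims to engage Veterans applying for compensation with pain conditions in multi-modal non-pharmacological pain care". Section 5.1 adds that counselors explain to unenrolled Veterans how to become eligible for VA care, and that they work through the PACT nurse and primary care provider. Section 9.2 reports a pilot rate ratio of 1.6 for pain-related appointments.

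Section 6.2.2 treats pain-driven and uneven visits as general weaknesses of the measure. It does not consider that they may differ by arm, and the statement in Section 9.6 leans the other way. If attendance depends on both arm and pain, the Veterans with a rating are no longer the randomized groups, and their ratings come at pain levels that treatment helped to select. A difference could then appear with no effect on pain, or a real effect could be hidden. The analysis restricted to Veterans with records would not repair this, because some enter VA care only after the compensation examination.

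The telephone assessments are at fixed times and are made by blinded research assistants (Section 6.2.3). An NRS asked there would not depend on clinic attendance.

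**Working it through.** **The plan's own figure.** None is stated for the NRS. The only yardstick is the BPI severity calculation in Section 9.2 (d = .25, alpha = .025, power = .90):

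n per arm = 2 × (2.241 + 1.282)² / 0.25² ≈ 397.2, rounded up to 398, against the stated 400. Then 400 / 0.73 = 548, and 548 × 2 = 1096. The figure reproduces. It does not bear on the NRS except as a scale for the sizes below.

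**Check 1: selection alone.** Let s be the share of an arm with a clinic rating, and g the mean difference in pain between Veterans seen and not seen. The mean among those seen exceeds the arm mean by g × (1 − s). The documents give neither s nor g. Assume s = 70% in SBIRT-PM and 55% in UC, g = 0.3 SD in both arms, and no true effect:

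- SBIRT-PM: 0.3 × 0.30 = 0.090 SD
- UC: 0.3 × 0.45 = 0.135 SD
- SBIRT-PM minus UC: −0.045 SD, a false benefit; 0.045 / 0.25 = 18% of the design effect for BPI severity

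The sign is not fixed. With the UC shift held at 0.135, it reverses once the gap in SBIRT-PM exceeds 0.135 / 0.30 = 0.45 SD, as could happen if counseling mainly draws in Veterans with high pain.

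**Check 2: selection and timing together.** This simulation had 200,000 Veterans per arm and no true effect on pain. All of these are assumptions not found in the documents:

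- pain with mean 5.5, between-person SD 1.5 and within-person SD 1.0 on the 0–10 scale, over 12 intervals
- Poisson visits, averaging 0.5, 1 or 2 per period in UC
- log visit rate rising by 0, 0.2 or 0.4 per NRS point
- 1.6 times the visits in SBIRT-PM, either as a proportional increase at every pain level or as extra visits unrelated to pain

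The 1.6 is borrowed from the pilot ratio for pain-related appointments. Each Veteran's clinic NRS is the average over visits attended.

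| Rise in log visit rate per point | Proportional increase, points (SD) | Extra visits regardless of pain, points (SD) |
|---|---|---|
| 0 | −0.006 to 0.002 (about 0) | −0.003 to 0.005 (about 0) |
| 0.2 | −0.058 to −0.073 (0.035 to 0.043) | −0.187 to −0.230 (0.114 to 0.133) |
| 0.4 | −0.103 to −0.130 (0.062 to 0.080) | −0.387 to −0.460 (0.244 to 0.276) |

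Ranges are over the three UC visit rates. Negative values falsely favour SBIRT-PM. The share with at least one rating was 37–86% in UC and 50–96% in SBIRT-PM. Pain measured for everyone, regardless of visits, differed between arms by no more than 0.015 points in any scenario.

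**The case against.** The strongest reply is that bias is possible but not shown. The documents give no visit rates and no relation between visits and pain, and the result is about zero if the two are unrelated. That stands. A reader might infer that the comparison is known to be biased in favour of SBIRT-PM; the documents do not support that.

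A reader might also infer that the intervention is designed to raise the visits at which the NRS is recorded. That goes too far. Its target is non-pharmacological pain care, while the rating comes from Primary Care vital signs. Counselors mostly write chart notes asking a provider to consider a consult or to take the matter up when the Veteran is next seen, which need not create a visit. The pilot ratio of 1.6 is for pain-related appointments, so its use above is an assumption. What remains is that help with VA eligibility and contact through PACT providers give a plausible route to differential attendance.

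The 0.045 SD figure is one assumed scenario, and it is small. With 70% and 55% of 550 per arm (385 and 302.5), the standard error of a difference is √(1/385 + 1/302.5) ≈ 0.077 SD, so 0.045 is about 0.6 standard errors.

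It may be inferred from Section 6.1 that interview NRS data exist. Only that table says so; no text describes an NRS telephone item, and self-report there could simply mean a patient-reported score. This has to be confirmed.

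Finally, the Précis wants telephone outcomes corroborated from the health record, and BPI severity and PEG already cover interview pain intensity. Corroboration is a fair purpose, but it can be served descriptively without a between-arm test.

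**Conclusion.** The concern holds as a risk and as an inconsistency. Section 6.2.2 and the schedule give different sources for the NRS, and Sections 3 and 9.5.2 omit an outcome that the Précis lists. As worded in Section 6.2.2, the arm comparison rests on ratings whose presence and timing treatment may affect, and the non-differential statement in Section 9.6 is not a safe basis for it.

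The size is unknown. Under the assumptions shown, it runs from about 0 to about 0.28 SD. The upper end needs both strongly pain-related visits and extra visits prompted regardless of pain. The scenarios computed are either null or favour SBIRT-PM, but the direction could be the opposite.

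The reach is limited to one secondary outcome. The primary BPI severity outcome, BPI interference and PEG are self-report measures scheduled at the telephone assessments and do not depend on clinic attendance.

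**What to change.** 1. Confirm that the NRS is asked at the telephone interviews, as Section 6.1 schedules.
2. If it is, name that self-report NRS at weeks 12 and 36 as the NRS secondary outcome in Section 6.2.2, list it in Sections 3 and 9.5.2, and analyse it with the BPI model of Section 9.6.
3. Keep the record-based NRS as a descriptive corroborating measure. Define its window, and report the number of Veterans with a rating and the number of ratings per arm.
4. If no interview NRS was collected, relabel the record-based NRS as exploratory and rest the between-arm pain comparison on BPI severity and PEG.
5. Qualify the non-differential statement in Section 9.6 so that it is not read as covering the NRS.

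The cost is wording, with no new data collection if the schedule is accurate. The record-based NRS loses its standing as a between-arm secondary outcome, and the interview NRS partly overlaps with BPI severity.
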